Neuromuscular blocking agents in the elderly

Protocol

An observational study of rocuronium 0.6 mg/kg comparing onset time, duration of action and effect on intubating conditions in younger (18 – 40 years) and elderly patients (> 80 years)

Version 1, December 6th 2018

Principal investigator

[name], PhD

Department of Anaesthesia, Centre of Head and Orthopedics, 4031 Rigshospitalet,

University of Copenhagen, Denmark

Sponsor

[name], PhD, DMSc

Department of Anaesthesia, Centre of Head and Orthopedics, 4031 Rigshospitalet,
University of Copenhagen, Denmark

Responsible department:

Department of Anaesthesia, Centre of Head and Orthopedics, 4031 Rigshospitalet,

University of Copenhagen, Denmark

Background

The number of elderly patients (>80 years) is increasing and a large proportion of these patients will require surgery and anesthesia within the next decades¹. Elderly patients are at higher risk of major morbidity and mortality² and are characterized by a reduction in cardiac output, liver function and renal function. These physiological changes influence pharmacodynamics and pharmacokinetics of drugs administered during anesthesia as for example neuromuscular blocking agents (NMBA).

During anesthesia NMBAs are used to facilitate tracheal intubation, establish muscle relaxation and suppress reflexes during surgery^{3–5}. Elderly patients are more sensitive towards muscle relaxants. In addition studies have reported prolonged duration of NMBAs^{6–8} and an observational study found that elderly patients are more prone to experience residual neuromuscular blockade in the post anesthesia care unit⁹. However, most studies have been conducted in elderly below 80 years^{7,10}.

It is unknown if there are differences in onset times of NMBAs e.g. rocuronium, mivacurium and cisatracurium between younger patients and elderly. Onset time for NMBAs in the elderly is of importance since it may influence intubating conditions, especially during rapid sequence induction. For example it is unknown in the elderly if an increased dose of NMBA reduces the onset time. There remains a need for studies investigating the optimal dose for facilitating intubation in the elderly, both during rapid sequence induction and during elective procedures.

The aim of this study is to determine the onset time, duration of action and effect on intubating conditions for rocuronium 0.6 mg/kg in patients aged 18-40 years and in patients with age > 80 years. The hypothesis of this study is that rocuronium administered in elderly patients (>80 years) has a longer onset in the elderly compared to younger patients.

Method:

Design:

Observational clinical study

Outcomes:

The primary end point is onset time, defined as the time from the end of rocuronium injection to Train-of-four (TOF) count of 0 monitored by acceleromyography.

The secondary endpoints are intubating conditions rated by an intubating difficulty scale¹¹ after 90 seconds and duration of action, defined as time from end of rocuronium injection to reappearance of TOF ratio > 0.9.

The pharmacodynamic data obtained are: time to reappearance of the T1, time to T1 recovery to 25% (of the final T1), and time to T0F ratio 0.90

Number of patients: 32 patients (16 in each group):

Group young: 16 patients receiving rocuronium 0.6 mg/kg

Group elderly: 16 patients receiving rocuronium 0.6 mg/kg

Doses are based on ideal body weight, calculated as height (cm) minus 105 for women and height (cm) minus 100 for men.

Inclusion criteria:

Patients > 18 years old

Informed consent

Scheduled for elective surgery (>1 hour) under general anaesthesia with intubation and use of rocuronium

3

American Society of Anesthesiologists (ASA) physical status classification I to III
Can read and understand Danish
Exclusion criteria:
Known allergy to rocuronium
Neuromuscular disease that may interfere with neuromuscular data
Indication for rapid sequence induction
End of study:
When 32 patients have been evaluated considering the primary endpoint the study is concluded
Pre-operative assessment:
In the Case Report Form (CRF) the following baseline data is noted:
Age
Sex
Weight
Height
BMI
ASA group (I-IV)
Co-morbidity

Perioperative treatment:

Monitoring:

The patient will be monitored with ECG, noninvasive blood pressure, oxygen saturation, and temperature sensors in nose cavity or bladder. Neuromuscular monitoring will be performed with TOF-Watch SX connected to a computer for collection of neuromuscular data (Version 2.5 INT 2007, Organon, The Netherlands). The monitoring will be done according to international guidelines¹³. TOF-Watch SX will be placed on the arm, where there is the least monitoring in general. Initially, the skin will be shaved and cleansed and rubbed with an abrasive. Small ECG electrodes will be used. They will be placed on the wrist over the ulnar nerve. The acceleration transducer will be placed on the thumb and attached in the associated hand adaptor. When the patient is adequately anesthetized we will start the TOF Watch SX and give two train-of-four (TOF) nerve stimulations followed by a tetanic stimulation with 50 Hz for 5 seconds. Then we will calibrate the TOF Watch SX with the CAL2 button and start the TOF mode and measure the TOF (2 Hz for 1.5 seconds) each 15 sec. After securing a stable signal with less than 5% deviation for two minutes we will inject rocuronium. When TOF = 0 we will measure the PTC for every 3-4 minutes.

An intravenous catheter will be placed in the opposite hand.

Anesthesia:

General anesthesia comprises induction with propofol 1-2 mg/kg and fentanyl 1.5-3.0 mcg/kg. Tracheal intubation is performed 90 seconds after administration of rocuronium 0.6 mg/kg. Anesthesia will be maintained with propofol approximately 5 mg/kg/hour and remifentanil 0.25-0.5 mcg/kg/min and adjusted according to depth of anesthesia.

Treatment values:

Blood pressure: Mean arterial pressure (MAP) max. 30 % difference from baseline.

Neuromuscular monitoring continues until TOF \geq 0.90 and stable over 2 min. In case of TOF < 0.90 at the end of surgery the NMB is reversed with neostigmine or sugammadex according to guidelines at the department. Subsequently, the patient is awakened and taken to the recovery room.

Intubating conditions:

Intubating conditions will be assessed 90 seconds after end of injection of rocuronium 0.6 mg/kg employing the Intubating Difficulty Scale. The scale comprises seven items:

N1-The number of supplementary attempts, an attempt defined as one advancement of the tube in the direction of the glottis during direct laryngoscopy or one like advancement of the tube in the case of a blind intubation trial.

N2-The number of supplementary operators; N2represents the number of additional persons directly attempting (i.e., not assisting) intubation.

N3-The number of alternative techniques used. For example, changing from an oral intubation to blind nasotracheal intubation or from a curved blade to straight blade increases N3by 1 point. The various techniques used should be noted in chronological order, so that subsequent identification of techniques ineffective in a particular case (or series) may be undertaken.

N4-Glottic exposure as defined by the Cormack grade [4] minus one; grade I (N4= 0) on this scale corresponds to complete visualization of the vocal cords, grade II (N4= 1) to visualization of the inferior portion of the glottis, grade III (N4= 2) to visualization of only the epiglottis, and grade IV (N4= 3) to a nonvisualized epiglottis. Glottic exposure is evaluated during the first attempt by the first operator. In case of successful intubation after blind nasotracheal intubation, N4= 0. If the blind attempt(s) fail, glottic exposure is evaluated during the first subsequent alternative visualized laryngoscopic attempt.

N5-The lifting force applied during laryngoscopy; N5= 0 if little effort is necessary, and N5= 1 if subjectively increased lifting force is necessary. This notion is based on the operator's impression that an abnormal amount of force was used compared with routine practice.

N6-The necessity of applied external laryngeal pressure for optimized the glottic exposure; N6= 0 if no external pressure is applied. N6= 1 if external laryngeal pressure is necessary. Application of the Sellick Maneuver is intended to inhibit aspiration of gastric contents and does not alter the score.

N7-Position of vocal cords; N7= 0 if vocal cords are in abduction. N7= 1 if the vocal cords are in abduction, presenting an impediment to tube passage. If the vocal cords are not visualized, N7= 0 by default.

Positioning:

The patient will be positioned with the arm with neuromuscular monitoring equipment in abducted position. It is ensured that the monitoring equipment is as unaffected as possible to achieve the most precise neuromuscular data. Intravenous cannula will be placed in opposite hand than neuromuscular monitoring equipment.

Surgery:

Surgery with use of rocuronium 0.6 mg/kg for intubation.

Respiratory:

Patients are oxygenated at FiO2=1.0 during preoxygenation and induction of anesthesia until the trachea is intubated. Anesthesia continues initially with FiO2=0.30. Patients are ventilated with Pressure Control Ventilation, tidal volume 7 ml/kg, PEEP (positive end-expiratory pressure) 5 cm H2O and respiration frequency 10-12 targeting normocapnia (ETCO2 at 4.5-5.5 kPa). If PaCO2> 6 kPa primarily the respiration frequency (RF) will be increased. If hypoxemia arises, defined as SpO2< 95 or PaO2< 10 kPa primarily FiO2 will be increased. In the event of deficient effect, PEEP will be increased.

Fluid therapy:

1000 ml Ringer lactate is given intraoperatively. Blood loss up to 500 ml is replaced with Ringer lactate 1:2.5. Blood loss in excess of this is replaced in accordance with the local guidelines.

In case of hypotension ephedrine or phenylephrine will be administered. In case of need for continuous inotropic infusion phenylephrine or noradrenalin will be used.

Antibiotics:

According to local guidelines. Dose and name will be noted on the CRF.

Pain treatment:

Postoperative pain treatment with paracetamol, fentanyl, morphine and peripheral nerve blocks according to local guidelines.

PONV treatment:

PONV prophylaxis and treatment with ondansetron, dexamethasone and droperidol according to local guidelines.

Data collection

Perioperative data collection that will be noted in CRF:

Type of operation with operation code

TOF values (NMB sheet)

Body temperature measured immediately after intubation and again immediately before extubation

Intubating difficulty score

Operating time (from incision to last suture)

Statistics:

Normal distributed variables will be expressed by means and standard deviations; variables that

are not normal distributed will be expressed by medians and interquartile ranges. Student's t-test

is used to compare normal distributed data and Mann-Whitney test to compare not normal

distributed data.

X2-test or Fisher's exact test will be used for frequencies when comparing the two groups.

Sample size:

We estimated a 20 seconds standard deviation for onset time of rocuronium based on previous

studies¹². We considered a difference in onset time of 30 seconds between the younger and

elderly groups to be clinically relevant. We have calculated that a sample size of 16 patients in

each group will allow us to detect this difference, with 5% Type 1 error risk and 90% power.

Schedule:

Inclusion of 2-3 patients per week is expected corresponding to duration of inclusion of

approximately 10-16 weeks. Inclusion: Planned to go on in the period from December 2018 to

April 2019. Inclusion of patients will be stopped when the desired number of patients is achieved.

The trial will be counted as concluded, when the last patient has registered with the primary

endpoint.

Data analysis and reporting: from April 2019 to June 2019.

Risks and side effects

Rocuronium: According to the product summary side effects are:

Not common (0,1-1%): Hypotension, anafylactic reaction.

Seldom (< 0,01%): Shock, angioedema, face edema.

9

Tracheal intubation with use of rocuronium is routinely performed at Department of Anaesthesia, Centre of Head and Orthopedics, 4031 Rigshospitalet. In both groups the patients will receive rocuronium in a dose aiming to provide optimal intubating conditions. It is not regarded as a disadvantage to use rocuronium, since the effect is monitored through surgery and if needed fully reversed by a reversal agent upon end of surgery.

Ethical considerations:

Tracheal intubation is as a standard performed with use of a rocuronium 0.6 mg/kg. Anesthesia and surgery will follow standard guidelines. The possible benefit in this trial is to investigate whether rocuronium 0.6 mg/kg has a different onset time in the elderly compared to younger patients. This may result in different intubating difficulty scores between younger and elderly patients. The results may help to detect the optimal dose of rocuronium for intubation of the trachea in elderly patients.

Consent and patient recruitment:

Patients are recruited among those referred to the Department of Anaesthesia, Centre of Head and Orthopedics, 4031 Rigshospitalet who meet inclusion criteria and who have no exclusion criteria.

The principal investigator is responsible for patient information and declaration of consent. In case the principal investigator is not able to interview the patient another investigator with GCP experience and medical knowledge within anaesthesia can perform the interview instead by referring to the principal investigator or sponsor. Written and oral patient information will be disclosed at the day of operation or 1-14 days before operation, during the preoperative anesthetic interview. This will be done in an undisturbed room. The patient will be offered the possibility of being accompanied by a family member or another person at the information interview. The patient will be informed that he/she will receive usual treatment if he/she does not want to participate, and that participation is voluntary, and that he/she always has the right to disclaim consent without affecting the further treatment.

After a period of consideration, depending on the patient's needs and maximum 30 minutes before operation, an attempt will be made to obtain consent.

Informed consent will be obtained before the patients arrive to the operation ward. We thereby wish to avoid putting the patients in a situation where they in a stress-full environment at the operation ward have to decide about participation in the trial.

The trial will be reported to the Scientific Ethics Committees, Danish Medicines Agency and Danish Data Protection Agency. The patients in the trial are assured access to receive further information about the trial through the principal investigator, who as contact person is referred to in the patient information. The "Forsøgspersoners rettigheder i et sundhedsvidenskabeligt forskningsprojekt (Rights of Trial Subjects)" published by the Scientific Ethics Committee will be provided. The trial will be considered as having started on the date when there is a signed declaration of consent from the first patient, who will thereby be considered as included. Conclusion of the study is when the last patient has been evaluated considering the primary outcome. At the end of the trial, investigator and sponsor will inform the Scientific Ethics Committee and the Danish Medicines Agency of this within 90 days. The trial will be registered in an international database (www.clinicaltrials.gov), before the recruitment of patients is started.

Quality control:

General procedures for quality control and quality assurance will be followed according to Good Clinical Practice guidelines.

Access to patients' journals

Upon granting of informed consent, principal investigator, sponsor, a representative of sponsor or third parties are authorized access to the patients' journal to find information regarding the patients' health conditions that are relevant for the conduction of the trial.

Data collection and storage:

Primary investigator will arrange for data collection and storage of CRFs in locked premises. Data will be stored for 5 years after conclusion of the trial. The information about the patients' health conditions, other purely private circumstances and other information that arises in connection with the trial is covered by the obligation of confidentiality. The information about the patients is protected by the Act on processing of personal information and the Danish Health Act.

Responsible department:

Department of Anaesthesia, Centre of Head and Orthopedics, 4031 Rigshospitalet,

University of Copenhagen, Denmark

Publication:

The results, either positive, negative or inconclusive, will be submitted for publication in an international, English-language journal. Authorship will occur in accordance with international Committee of Medical Journal Editors' rules (the Vancouver Group). The right to data and knowhow that emerges in connection with the trial will belong to the trial coordinator and the Department of Anaesthesia, Centre of Head and Orthopedics, 4031 Rigshospitalet, University of Copenhagen, Denmark.

Registration:

The study will be registered at www.clinicaltrials.gov

Economy:

Principal investigator and sponsor have taken the initiative to this trial.

Expenses in the trial are covered by departmental sources and covers salary for study investigators.

Patients participating in the trial will not receive financial compensation.

Patients participating in this trial are covered by the insurance "Patienterstatningsordningen" and "Ordningen om erstatning for lægemiddelskader".

References:

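### Duration of action is not tied to spontaneous recovery, so post-reversal times count as the drug's duration; the age comparison can be biased, mainly if means are used

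*Combined protocol and SAP*

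**What the plan says.** - **Definition.** The protocol's Outcomes section lists, as one of two secondary endpoints, "duration of action, defined as time from end of rocuronium injection to reappearance of TOF ratio > 0.9". It does not say whether recovery must be spontaneous. The same section lists further recovery times, among them "time to T1 recovery to 25% (of the final T1), and time to T0F ratio 0.90", also without that condition.
- **Reversal.** Under Treatment values: "In case of TOF < 0.90 at the end of surgery the NMB is reversed with neostigmine or sugammadex". The Risks and side effects section repeats that the block is reversed at the end of surgery if needed.
- **Monitoring.** "Neuromuscular monitoring continues until TOF" reaches 0.90 and is stable for 2 minutes. So a TOF time can be read for reversed patients too.
- **Analysis.** The Statistics section says that the t-test "is used to compare normal distributed data and Mann-Whitney test to compare not normal" data, with means for the former; variables that "are not normal distributed will be expressed by medians and interquartile ranges". It gives no rule for choosing between the two routes and none for reversed patients.
- **Operation length.** Inclusion asks for planned surgery of more than one hour. There is no upper limit and no balancing of operating time between age groups.
- **Hypothesis.** It concerns onset only: that rocuronium "has a longer onset in the elderly compared to younger patients".

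**The concern.** Reversal is triggered by the outcome itself. Only patients who have not recovered by the end of surgery are reversed, so for them the drug's own duration is known only to be longer than the time of reversal. The stated definition replaces it with a time that depends on when surgery ended and how fast the reversal agent worked.

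The Background expects longer block and more residual block in older patients, so unequal reversal between the groups is plausible. With similar operation lengths, this shortens the elderly times more and pulls the difference towards zero. With operation lengths that differ by age, the error can go either way.

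Duration of action is in the title and the aim, so readers will look for this comparison. The endpoint is unpowered, however, and neither the hypothesis nor the sample size rests on it.

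**Working it through.** The plan states no figure for duration of action that could be reproduced: its SD of 20 s and difference of 30 s are for onset. What follows is an illustration on assumed values.

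**Assumptions.** True duration T is log-normal with CV 30% and medians of 60 min (young) and 90 min (elderly). Surgery ends at S = 20 min from injection to incision + an operating time uniform on 60-120 min. TOF 0.9 is reached at most 8 min after reversal.

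**True difference.** The log-scale variance is ln(1 + 0.30²) = 0.0862, so mean = median × √1.09 = median × 1.044. The means are 62.6 and 94.0 min. The mean difference is 30 × 1.044 = 31.3 min and the median difference is 90 − 60 = 30.0 min.

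**What the plan would record.** A patient is reversed if T > S. The recorded time is min(T, S + 8). Simulation gives 4% of young and 29% of elderly reversed. Recorded means fall by about 0.3 min in the young and 5.0 min in the elderly, so the mean difference becomes 31.3 − 5.0 + 0.3 = 26.6 min.

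**Why the median holds.** A reversed elderly patient moves below the true median of 90 min only if S + 8 < 90, that is S < 82. As S runs from 80 to 140, that has probability 2/60. Half of the patients have T > 90, so 2/60 × 0.5 = 1.7% cross the median. With 0 min to incision (S from 60 to 120), 22/60 × 0.5 = 18% cross and the median moves materially.

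**Variations**, with post-reversal times counted (simulation error up to about 0.2 min):

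| Medians, young/elderly | Operation, min | Min to incision | Elderly reversed | True mean / median difference | Counted mean / median difference |
|---|---|---|---|---|---|
| 60/90 | 60-120 | 20 | 29% | 31.3 / 30.0 | 26.6 / 29.2 |
| 60/90 | 60-120 | 30 | 20% | 31.3 / 30.0 | 28.3 / 30.1 |
| 60/90 | 60-120 | 0 | 52% | 31.3 / 30.0 | 21.3 / 21.0 |
| 60/90 | 60-240 | 20 | 10% | 31.3 / 30.0 | 29.6 / 29.7 |
| 60/90 | 120-240 | 20 | 1% | 31.3 / 30.0 | 31.2 / 30.0 |
| 50/75 | 60-120 | 20 | 14% | 26.1 / 25.0 | 24.5 / 25.0 |
| 40/60 | 60-120 | 20 | 4% | 20.9 / 20.0 | 20.6 / 20.0 |

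For 50/75 the mean loss is 26.08 − 24.53 = 1.55 min before rounding. In the first row, varying the CV over 20-40% and recovery after reversal over 2-15 min gives a counted mean difference of 23.1-29.4 (true 30.6-32.4) and a counted median difference of 26.6-30.1 (true 30.0).

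**Tests**, 4,000 simulated trials of 16 per group. In the first row, Mann-Whitney power is 96.0% on true durations and 95.7% on counted times; log-rank with censoring at reversal has 94.3%. With no true difference (both medians 75) and operations of 60-120 min in the young and 60-180 min in the elderly, the spurious mean difference is +0.8 min and the Mann-Whitney type I error 4.7%. An extreme case (young 60-90, elderly 120-240 min, 0 min to incision, 51% of young reversed) raises the Mann-Whitney type I error to 11.8%, against 5.2% for log-rank. At 20 min to incision (22% of young reversed) it is back to 5.2%.

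**Which route applies** is open. If Shapiro-Wilk at 5% in each group were used (an assumption), 83% of first-row trials would go to means and the t-test, the more sensitive route.

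**The case against.** The best defence is that the definition is complete as written: everyone is monitored to 0.90, everyone has a time, and that time is compared. On this reading medians and Mann-Whitney hardly move unless about half of a group is reversed. Reaching that in the illustration took 0 min from injection to incision, which is unrealistic when intubation alone comes 90 seconds after rocuronium. The larger mean losses depend on assumed medians of 60 and 90 min, and the requirement of more than one hour of surgery limits reversals. Most of this stands, and it sets the weight of the point. It does not remove the point: the literal endpoint mixes the drug's duration with operation length and reversal effect, and the plan leaves the mean and t-test route open.

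Three stronger readings are tempting but unsupported:

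- *Two analysts following the text could report about 27 or about 21 min.* The 21 comes from excluding reversed patients, which the text does not call for.
- *Reversal data will not be collected.* The Data collection list does not name the agent or its time, but the list is not exhaustive: the antibiotic's name and dose go on the CRF under a different heading.
- *Censoring would raise power.* In the illustration it does not.

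Monitoring follows cited international guidelines, but the protocol states no rule for reversed patients taken from them.

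**Conclusion.** The point holds as a minor one. The age difference in duration of action can be biased because reversed patients' post-reversal times count as the drug's duration. The exposure is mainly in means and the t-test: about 31 min becomes about 27 under the main assumptions, with a loss of about 1.5 min or less for shorter assumed durations and a negligible one when operations far outlast the block. Material distortion of medians and Mann-Whitney needs about half of a group reversed, although very quick recovery after reversal can lower the median difference somewhat sooner (to 26.6 of 30.0 at worst in the range tried). Every size rests on assumed durations, operation lengths and recovery times. A reader should not infer that the comparison is known to be biased, or in which direction: that depends on the number reversed in each group. Onset time and its sample size are untouched, because onset comes before any reversal.

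**What to change.** - **Define** duration of action as time to spontaneous TOF ratio 0.9. Right-censor at the time a reversal agent is given. Compare groups with Kaplan-Meier estimates and a log-rank test.
- **Rule out exclusion** of reversed patients for this endpoint. It would remove the longest durations (mean difference about 21 instead of 31 min under the main assumptions), and they would not be replaced, since the study ends once 32 patients have the primary endpoint.
- **Other recovery times:** apply the same censoring when they are not reached before reversal.
- **T1 25% needs its own sentence.** It is scaled to the final T1, which in a reversed patient is measured after reversal even if the 25% point came earlier. State that such a value is not a spontaneous reference, and either report this measure in unreversed patients only, labelled as such, or pre-specify another reference.
- **Record** the reversal agent and its time. **Report** by group the number reversed and the time from injection to end of surgery, so that readers can judge whether censoring matters.

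The cost is a few sentences in Outcomes and Statistics and two CRF fields if these are not already there. Reversal practice does not change. There are three downsides. The Kaplan-Meier median may not be reached: in under 1% of simulated trials with 29% of elderly reversed, 9-18% with 44-52% of a group reversed, and 62% with 72%. Log-rank power is about equal to, or up to about 2 points below, Mann-Whitney on counted times when operations are equal. And censoring assumes that the end of surgery is unrelated to recovery within each group.

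### The total Intubating Difficulty Scale, the only measure of rocuronium's effect on intubating conditions, says little that is specific to block at 90 seconds, so a group difference in it cannot be attributed to onset.

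*Combined protocol and SAP*

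**What the plan says.** The aim, stated just before the Method section, is to "determine the onset time, duration of action and effect on intubating conditions for rocuronium 0.6 mg/kg" in patients aged 18 to 40 and patients over 80. Under Outcomes, "The primary end point is onset time, defined as the time from the end of rocuronium injection to Train-of-four (TOF) count of 0". Intubating conditions come next: "The secondary endpoints are intubating conditions rated by an intubating difficulty scale".

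The Intubating conditions section fixes the instrument and the time: "Intubating conditions will be assessed 90 seconds after end of injection of rocuronium 0.6 mg/kg employing the Intubating Difficulty Scale". It then defines seven items. N1 counts extra attempts. The next two are "N2-The number of supplementary operators" and "N3-The number of alternative techniques used". N4 is the Cormack grade minus one, N5 subjective lifting force, N6 external laryngeal pressure and N7 vocal cord position.

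The Data collection list has a single entry for all of this, the difficulty score. The Pre-operative assessment list holds age, sex, weight, height, BMI, ASA group and co-morbidity. The exclusion criteria do not mention a difficult airway. Ethical considerations raises the possibility that onset differs by age and continues: "This may result in different intubating difficulty scores between younger and elderly patients".

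**The concern.** The question is whether 0.6 mg/kg has relaxed older patients as well as younger ones by 90 seconds. The IDS sums how hard the whole intubation was. Its total can rise for reasons unrelated to block, and it can stay at zero when the patient coughs or moves as the tube passes.

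The groups are defined by age and lie at least 40 years apart (over 80 against 18 to 40). Anything about the airway that differs with age therefore enters the comparison, and nothing on the baseline list would allow it to be examined. At stake is the interpretation of a secondary endpoint that appears in the study title. A higher score in the elderly could be read as slow onset, and a similar score as reassurance. The protocol also hopes that its results will inform dosing in elderly patients, which makes either misreading more consequential.

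**Working it through.** The protocol gives no calculation for the IDS. Its only sample-size figure, 16 per group, concerns onset time and does not bear on this point. The check is of the content of the scale.

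**Items as defined in the Intubating conditions section**

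| Item | What it scores | Points | Direct link to relaxation |
|---|---|---|---|
| N1 | Extra attempts | no stated ceiling | no |
| N2 | Extra operators | no stated ceiling | no |
| N3 | Changes of technique | no stated ceiling | no |
| N4 | Glottic view | 0 to 3 | no |
| N5 | Lifting force, operator's impression | 0 or 1 | partly |
| N6 | External laryngeal pressure | 0 or 1 | no |
| N7 | Cord position | 0 or 1 | yes |

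The last column is my reading; the protocol does not say what drives each item.

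1. **Weight.** The bounded items total 3 + 1 + 1 + 1 = 6 points. N5 and N7 supply 1 + 1 = 2 of them. N1 to N3 come on top without limit.
2. **Coverage.** None of the seven items scores jaw relaxation, coughing or limb movement.
3. **Timing.** N4 is fixed at the first attempt by the first operator. N1 to N3 can score only after that attempt, so the total is not purely a 90-second observation.
4. **N7.** Both levels are printed as abduction, so the item most directly tied to paralysis cannot be scored as written. It is also 0 by default when the cords are not seen. By the protocol's own grades that covers Cormack III (epiglottis only) and IV (epiglottis not seen).

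**Two patients scored by these rules**

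- Fully blocked, Cormack III, laryngeal pressure needed: N4 = 3 − 1 = 2 and N6 = 1, so the total is at least 3.
- Complete view, little lifting effort, open cords, one attempt, one operator, one technique, but coughing and moving as the tube passes: N1 to N7 are all 0, so the total is 0.

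These show what the rules permit, not how often it happens.

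**Illustration with assumed rates (none is in the documents), 16 per group, 5% two-sided**

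- N7 compared alone by Fisher's exact test. Power is 10% for rates of 5% against 20%, 57% for 5% against 40%, and 91% for 5% against 60%.
- Total IDS compared by Mann-Whitney test, simulated 3,000 times. Assumptions in both groups: Cormack I to IV in 65%, 27%, 7% and 1%; laryngeal pressure in 20%; one or two points from N1 to N3 in 10%; N5 and N7 at 5% in the young.
  - No difference between groups: about 4% significant.
  - N7 raised to 40% in the elderly: about 17%, against 57% for N7 alone.
  - N5 and N7 both raised to 40%: about 44%.
  - Only the Cormack distribution shifted in the elderly, to 45%, 37%, 15% and 3%, with no difference in N5 or N7: about 13%.

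Under these assumptions the total dilutes a real difference in cord position, and it responds to a change in view nearly as often. Other rates would give other figures. The conclusion rests on the item content, not on this illustration.

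**The case against.** The strongest defence is that the IDS is a published, cited scale used for a secondary endpoint, while block itself is measured directly. Onset is timed by acceleromyography, and the hypothesis and sample size concern onset alone. That stands, and it limits the consequence of this point.

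A reader might infer that the scale cannot show an effect of rocuronium at all. The documents do not support that. N5 and N7 can respond to incomplete block, and closed cords or a failed first pass would raise N1 to N3. The Background says that relaxants facilitate intubation, and it cites a cohort study whose title links avoiding them to difficult intubation. The scale is insensitive and non-specific, not incapable.

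A reader might also infer that view, pressure and attempts are mainly matters of anatomy, or that elderly airways are known to differ. The protocol says neither, and the point does not need it. It is enough that the groups were not randomised and that no airway information is listed with which to look.

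Nor is the sentence in Ethical considerations a planned analysis. It says only that scores may differ, within a statement of possible benefit. The objection here is to reading a result that way.

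Finally, a rating of jaw tone, cough and movement is not free of confounding either. It also depends on depth of anaesthesia, induction doses span a twofold range (propofol 1 to 2 mg/kg, fentanyl 1.5 to 3.0 mcg/kg), and the operator can see the patient's age. This stands as a limit on the remedy.

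**Conclusion.** The point holds in a limited form. The total IDS is the only measure of one of three aims, and it gives limited, non-specific information about block at 90 seconds. Two of seven items, worth at most 2 points, relate directly to relaxation. One of those two cannot be scored as printed, and none of the seven covers jaw relaxation, cough or limb movement. A difference in total IDS between these non-randomised age groups cannot be attributed to onset, and the absence of one does not exclude poorer relaxation in the elderly.

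This rests on the item definitions and data lists in the protocol, and on the judgement that N5 and N7 are the items most directly tied to relaxation. It does not rest on any assumed rate. The TOF-based primary comparison is untouched, so this is a change that should be made rather than one on which the study depends.

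**What to change.** - Keep the IDS and report it as intubation difficulty.
- At the same first laryngoscopy, have the same operator record, with defined levels, jaw relaxation, cord position or movement, and cough or limb movement at tube passage. In Outcomes, name this first-attempt rating as the secondary endpoint for rocuronium's effect on intubating conditions, and state in Statistics how it will be compared.
- Correct N7 against the scale's source publication so that its two levels differ.
- Record the IDS items individually, and report first-attempt N5 and N7 separately.
- Note any routine preoperative airway assessment in the case report form.
- State that a difference in total IDS will not be interpreted as an effect of onset, and bring the sentence in Ethical considerations into line.

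The cost is a few case report form items, short definitions of the rating levels, and one more secondary result, which is subjective, unblinded to age and also influenced by depth of anaesthesia. No extra staff or procedure is needed. The change has to precede recruitment, because reactions not recorded at the first laryngoscopy cannot be recovered. If the rating is not added, the minimum is to rename the endpoint intubation difficulty, correct N7 and drop the attribution to onset.
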